## Physiologic Pacing Registry Clinical Plan

### APPENDIX IV: SUMMARY

Registry Name	Physiologic Pacing Registry
Title	Physiologic Pacing – Post Market Registry
Purpose	The Physiologic Pacing Registry will be conducted to gain a deeper understanding of physiologic pacing device implants and follow-up workflows, including device and programmer measurements to help inform Abbott’s product and clinical data development efforts. Additionally, the registry will provide a broader understanding of the clinical utility in mapping physiologic pacing structures with the use of Abbott’s EnSite Cardiac Mapping System with an electrophysiology catheter prior to device implants for those institutions where mapping is routine care prior to physiologic pacing device implant.
Objective(s)	The Physiologic Pacing Registry will characterize implant and follow-up measures associated with physiologic pacing device implants. The registry will also compare implant and follow-up characteristics for implants performed with and without utilizing the EnSite Cardiac Mapping System.
Devices Included in Registry	Any market-approved Abbott pacemaker, defibrillator, or CRT device Any market-approved implant tools EnSite Cardiac Mapping System (optional)
Number of Subjects Required	[REDACTED]
Registry Design	This registry is designed as a prospective, non-randomized, multi-center registry. The registry will enroll patients scheduled for implant with an Abbott device with any available lead and associated implant tools – this is to ensure proper device data collection for future software and other physiologic pacing product development. Prior to device implant, investigators may perform a comprehensive electrophysiology study and/or create a 3-dimensional electro-anatomical map of physiologic pacing structures based on their site’s routine care using any diagnostic mapping catheter with the EnSite Cardiac Mapping System.

## Physiologic Pacing Registry Clinical Plan

Primary Outcomes Measure(s)
	
The Physiologic Pacing Registry will collect data on the following measures to characterize the workflow associated with physiologic pacing device implants and follow-up, and to quantify the clinical utility of mapping the physiologic pacing structures prior to implants according to sites' routine care. Implant and follow-up characteristics will be compared with and without utilizing the EnSite Cardiac Mapping System during device implants.
 
Implant Characteristics:
 
 
• Fluoroscopy time and radiation dose
 
• Overall procedure time: skin-to-skin
 
• Implant procedure time: vascular access to lead fixation
 
• All implant tools used
 
• Implant-related workflow
 
• Final implanted hardware
 
• Final post-procedure device programming
 
• Procedure- and device-related adverse events, and device deficiencies
 
• Implant success
 
• All types of physiologic pacing capture observed such as selective and non-selective
 
• Physiologic pacing capture and sensing thresholds
 
• Pacing output necessary to correct bundle branch block using 12-lead ECG (if applicable)
 
• QRS duration for all types of physiologic pacing captures observed using 12-lead ECG
 
• For His placement only: Measured H wave using device intracardiac electrogram (IEGM)
 
• Measured R wave using device IEGMs through physiologic pacing lead
 
 
Follow-up Characteristics:
 
 
• Follow-up related workflow
 
• Physiologic pacing capture and sensing thresholds
 
• For His placement only: Measured H wave using device IEGM
 
• Measured R wave using device IEGMs through physiologic pacing lead
 
• QRS duration for all types of physiologic pacing captures observed using 12-lead ECG
 
• Presenting QRS Duration and PR interval using 12-lead ECG
 
• Incidence of increase in capture threshold of > 1V in physiologic or RV pacing leads
 

---	--

## Physiologic Pacing Registry Clinical Plan

	
 
• Far-field atrial oversensing and ventricular oversensing and/or any interventions – including programming – required to address these issues
 
• NYHA Classification
 
• LVEF, LVEDV, LVESV (if available)
 
• Tricuspid and mitral regurgitation severity by echocardiogram (if available)
 
• Device estimated battery longevity via device session records
 
• Frequency/burden of detected atrial and ventricular arrhythmias via device session records
 
• Procedure and device-related adverse events, and device deficiencies
 

Subject Follow-up	The subjects will be followed in-clinic at baseline (before implant), implant, and at 1 month and 6 months after the date of successful implant.

## Physiologic Pacing Registry Clinical Plan

Inclusion Criteria	
 
• Scheduled for implantation of an Abbott pacemaker, defibrillator, or CRT-P/D device with a pacing lead located at a physiologic pacing structure according to the clinical site’s standard of care
 
• At least 18 years of age
 
• Willing and able to comply with the prescribed follow-up tests and schedule of evaluations
 
• Provided written informed consent prior to any registry-related procedure
 

Exclusion Criteria	
 
• History of tricuspid valve repair or replacement
 
• Currently participating in another clinical study with an active treatment arm and belong to the active arm
 
• Presence of other anatomic or comorbid conditions, or other medical, social, or psychological conditions that, in the investigator’s opinion, could limit the subject’s ability to participate in the registry or to comply with follow-up requirements, or impact the scientific soundness of the registry results
 
• Chronic physiologic pacing lead implanted
 
• Life expectancy of < 6 months
 
• Known contraindication for a physiologic pacing implant (i.e. ongoing infection, known occlusion of the subclavian vein, etc.)
 

NCT Number: NCT03719040
CRD955 PP Registry
Physiologic Pacing Registry
Study Document No: < ABT-CIP-10270>
Version A
Date: 5-April-2021

Sponsor

Abbott
[name]
[name]
USA

Protocol [REDACTED]
CRD955 PP Registry

Physiologic Pacing Registry

Statistical Analysis Plan (SAP)

[REDACTED]

[REDACTED]

[REDACTED]

TABLE OF CONTENTS

1.0	SYNOPSIS OF STUDY DESIGN	4
1.1	Purpose of the Statistical Analysis Plan	4
1.2	Clinical Investigation Objectives.....	4
1.3	Clinical Investigation Design	4
1.4	Endpoints.....	4
2.0	ANALYSIS CONSIDERATIONS.....	6
2.1	Analysis Populations.....	6
2.1.1	Enrollment Population.....	6
2.1.2	Implanted Population	6
2.2	Statistical Methods.....	6
2.2.1	Descriptive Statistics for Continuous Variables	6
2.2.2	Descriptive Statistics for Categorical Variables	7
2.2.3	Survival Analyses	7
2.3	Endpoint Analysis	7
2.3.1	Implant Characteristics	7
2.3.2	Follow-up Characteristics.....	7
2.4	Sample Size Calculations	7
2.5	
2.6	
2.7	Subgroups for Analysis	7
2.8	Handling of Missing Data	8
3.0	DESCRIPTIVE ENDPOINTS AND ADDITIONAL DATA.....	8
3.1	Baseline and Demographic Characteristics.....	8
3.2	Adverse Events.....	8
3.3	Subject Early Termination.....	8
3.4	Protocol Deviation.....	8
4.0	DOCUMENTATION AND OHER CONSIDERATIONS	8
5.0	ACRONYMS AND ABBREVIATIONS.....	9
6.0	REFERENCES.....	10

1.0 **SYNOPSIS OF STUDY DESIGN**

1.1 **Purpose of the Statistical Analysis Plan**

This statistical analysis plan (SAP) is to provide a detailed and comprehensive description of the planned methodology and analysis to be used in the Physiologic Pacing (PP) registry study. This plan is based on the version C of Clinical Investigational Plan (CIP).

1.2 **Clinical Investigation Objectives**

The PP Registry will characterize the implant and follow-up measures associated with physiologic pacing device implants. The registry will also compare the implant and follow-up characteristics for these device implants with and without utilizing the EnSite Cardiac Mapping System, based on the sites' routine care. Data on all tools used as chosen by the physicians as part of their standard practice will be collected. Abbott will collect data based on the characteristics at implant and follow-up.

1.3 **Clinical Investigation Design**

The PP Registry is a prospective, observational, multi-center registry designed to characterize device data at implant and follow-up in patients with a permanent physiologic pacing lead and an Abbott pacemaker, defibrillator, or CRT-P/D. The devices selected for use will be at the discretion of the implanting physician.

The registry will enroll up to 1,000 subjects from up to 75 participating centers worldwide.

The total duration of the registry is expected to be 4 years, including enrollment and data collection from all subjects.

1.4 **Endpoints**

The PP Registry will collect data on the following measures as recommended by the His Bundle Pacing Collaborative Working group¹ to characterize the workflow associated with physiologic pacing device implants and follow-up, and to quantify the clinical utility of mapping the cardiac structures prior to physiologic pacing device implants according to sites' routine care. Implant and follow-up characteristics will be compared with and without utilizing the EnSite Cardiac Mapping System during device implants.

Implant Characteristics:

- Fluoroscopy time and radiation dose

- Overall procedure time [REDACTED]
- Implant procedure time [REDACTED]
- All implant tools used
- Implant-related workflow
[REDACTED]
- Final implanted hardware
- Final post-procedure device programming
[REDACTED]
- Procedure- and device-related adverse events and device deficiencies
- Implant success [REDACTED]
[REDACTED]
- All types of physiologic pacing capture observed such as selective and non-selective
- Physiologic pacing capture and sensing thresholds
- Pacing output necessary to correct bundle branch block using 12-lead ECG (if applicable)
- QRS duration at baseline and following implant using 12-lead ECG
- QRS duration for all types of physiologic pacing captures observed using 12-lead ECG
- For His placement only: Measured H wave using device IEGM
- Measured R wave using device IEGMs through the lead implanted for physiologic pacing

Follow-up Characteristics:

- Follow-up related workflow
- Physiologic pacing capture and sensing thresholds
- For His placement only: Measured H wave using device IEGM
- Measured R wave using device IEGMs through the lead implanted for physiologic pacing
- Presenting PR interval and QRS duration using 12-lead ECG
- QRS duration for all types of physiologic pacing captures observed using 12-lead ECG

- Incidence of increase in capture threshold of > 1V in leads implanted for physiologic pacing or RV pacing leads
- Far-field atrial oversensing and ventricular oversensing and/or any interventions – including programming – required to address these issues
- NYHA Classification
- LVEF, LVEDV, LVESV (if available)
- Tricuspid and mitral regurgitation severity by echocardiogram (if available)
- Device estimated battery longevity via device session records
- Frequency/burden of detected atrial and ventricular arrhythmias via device session records
- Procedure and device-related adverse events

2.0 **ANALYSIS CONSIDERATIONS**

2.1 **Analysis Populations**

2.1.1 **Enrollment Population**

The enrollment population includes all subjects enrolled (upon providing written informed consent) in the registry.

2.1.2 **Implanted Population**

The implanted population includes subjects enrolled in the registry, implanted with Abbott device, and have an active (programmed on) lead implanted for physiologic pacing post implant.

2.2 **Statistical Methods**

Descriptive analysis will be performed to summarize baseline, procedural, safety and effectiveness endpoints and clinical safety event data. Depending on the type of data (e.g. continuous or categorical), statistical methods described in this section below will be used.

2.2.1 **Descriptive Statistics for Continuous Variables**

For continuous variables (e.g., age, blood pressure, 12-lead ECG, etc.), results will be summarized with the numbers of observations, means, and standard deviations, and in addition, with medians, quartiles, minimums, maximums. The 95% confidence intervals may also be provided for the means, when specified.

2.2.2 Descriptive Statistics for Categorical Variables

For categorical variables (e.g. sex, NYHA class, etc.), results will be summarized with subject counts and percentages/rates. The exact 95% Clopper-Pearson² confidence intervals may also be provided when specified.

2.2.3 Survival Analyses

Survival analysis will be conducted to analyze time-to-event variables. Subjects without events will be censored at their last known event-free time point. Survival curves will be constructed using Kaplan-Meier estimates.

2.3 Endpoint Analysis

2.3.1 Implant Characteristics

There is no pre-specified hypothesis testing for the implant characteristics. All the implant characteristics will be summarized descriptively.

2.3.2 Follow-up Characteristics

There is no pre-specified hypothesis testing for the follow-up characteristics. All the follow-up characteristics will be summarized descriptively at 1-month and 6-month.

2.4 Sample Size Calculations

There is no hypothesis testing in this registry. Therefore, no formal sample size calculation has been performed.

2.5 [REDACTED]

2.6 [REDACTED]

2.7 Subgroups for Analysis

Major implant characteristics will be summarized by subgroups, which include but are not limited to the following:

- Ensite Mapping system used to identify His signal [REDACTED]
- Physiologic pacing mode [REDACTED]

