## Physiologic Pacing Registry Clinical Plan

### 2.0 CLINICAL REGISTRY OVERVIEW

#### 2.1 Objectives

##### 2.1.1 Primary objective

The Physiologic Pacing Registry will characterize implant and follow-up measures associated with physiologic pacing device implants. The registry will also compare implant and follow-up characteristics for these device implants with and without utilizing the EnSite Cardiac Mapping System, based on the site's routine care. Data on all tools used as chosen by the physician as part of their standard practice will be collected. Abbott will collect data on the following characteristics at implant and follow-up:

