### 4.0 ENDPOINTS

#### 4.1 Registry Outcome Measures

The Physiologic Pacing Registry will collect data on the following measures as recommended by the His Bundle Pacing Collaborative Working group to characterize the workflow associated with physiologic pacing device implants and follow-up, and to quantify the clinical utility of mapping the cardiac structures prior to physiologic pacing device implants according to sites' routine care. Implant and follow-up characteristics will be compared with and without utilizing the EnSite Cardiac Mapping System during device implants.

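### The promised comparison with and without EnSite mapping is not matched by the readable SAP methods: only major implant characteristics are split by mapping, follow-up has no stated split, and the contrast is crude although mapping follows site or physician routine

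*SAP*

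**What the plan says.** **The promise.** Under its primary objective (2.1.1) the protocol says "The registry will also compare implant and follow-up characteristics for these device implants with and without utilizing the EnSite Cardiac Mapping System". Section 4.1 gives the aim as to "quantify the clinical utility of mapping the cardiac structures prior to physiologic pacing device implants". The primary outcomes row of Appendix IV says "Implant and follow-up characteristics will be compared with and without utilizing the EnSite Cardiac Mapping System during device implants". SAP 1.2 repeats the commitment ("The registry will also compare the implant and follow-up characteristics for these device implants with and without utilizing the EnSite Cardiac Mapping System"), and so does SAP 1.4.

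**The method.** SAP 2.2 announces a descriptive analysis and adds that "statistical methods described in this section below will be used". The readable methods are summary statistics for continuous and categorical variables, optional confidence intervals for means and percentages, and Kaplan-Meier curves. SAP 2.3.1 says "All the implant characteristics will be summarized descriptively". SAP 2.3.2 says "All the follow-up characteristics will be summarized descriptively at 1-month and 6-month". The only readable split by mapping is in SAP 2.7: "Major implant characteristics will be summarized by subgroups, which include but are not limited to the following". The mapping line there refers to EnSite being used to find the His signal; the rest of the line is redacted.

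**How mapping is chosen.** Appendix IV calls the design non-randomized. Protocol 1.1.2 ties mapping to institutions where it is routine, and 3.1 and 6.2 tie it to the physician's routine practice.

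**What cannot be read.** SAP 2.5 and 2.6, the ends of both lines in SAP 2.7, and protocol 8.2.1 (primary outcome analyses), 8.5 (subgroups), 8.6 (multiplicity) and 8.7 (pooling).

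**The concern.** Two things do not fit together.

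First, the SAP commits to a comparison in 1.2 and 1.4 that its readable methods deliver only in part. The open-ended wording in 2.7 extends the list of subgroups, not the list of characteristics, which stays at the major implant ones. The label of the mapping subgroup may also be narrower than with versus without EnSite. Protocol 1.1.2 foresees mapping of the left bundle branch as well, so the place of those cases is unclear.

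Second, the registry wants to put a value on mapping, but the readable output is a side-by-side table. If mapped cases come from different sites, operators and patients, a difference in fluoroscopy time, procedure time or implant success may reflect those differences and still be read as the benefit of mapping. Leaving out hypothesis tests does not help, because the bias lies in the crude difference itself.

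**Working it through.** The documents give no effect size, SD, mapped share or site correlation, so there is no figure of the plan to reproduce. The check has three steps.

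**Step 1. Promise against readable method**

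| Item | Promised (protocol 2.1.1, 4.1, App. IV; SAP 1.2, 1.4) | Readable method (SAP 2.3.1, 2.3.2, 2.7) |
|---|---|---|
| Implant characteristics | Compared by mapping | All summarized; major ones split by mapping |
| Follow-up characteristics | Compared by mapping | Summarized at 1 and 6 months; no mapping split named |
| Mapped group | EnSite used or not | EnSite used to find the His signal (line cut off) |
| Adjustment, site effect, estimate of the difference | Not stated | None readable |

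The conflict therefore lies inside the SAP as well: 1.2 and 1.4 against 2.3.2 and 2.7.

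**Step 2. Size of the bias from case mix (illustration; inputs assumed)**

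Bias in the crude difference = gap in prevalence of a baseline factor × its effect on the outcome. With an assumed effect of 0.5 SD and no true effect of mapping:

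- gap of 10 points: 0.10 × 0.5 = 0.05 SD
- gap of 20 points: 0.20 × 0.5 = 0.10 SD
- gap of 40 points: 0.40 × 0.5 = 0.20 SD

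**Step 3. Which model removes confounding by site (illustration; inputs assumed)**

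SAP 1.3 gives maxima of 1,000 subjects and 75 sites, so m = 1,000/75 = 13.3 per site. Assume total variance 1, ICC 0.10 (site SD √0.10 = 0.316, residual variance 0.90), half of the cases mapped, a correlation of 0.5 between the site effect and the site's mapping rate, and no true effect.

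- *Each site maps all or none.* Crude bias = 0.5 × 0.316 / 0.5 = 0.316 SD, where the divisor is the SD of a 50/50 indicator. There is no within-site information, so a random-intercept model has the same bias. Simulation gave 0.319 SD for both.
- *Site rates vary widely* (Beta(0.5, 0.5), variance 0.125, SD 0.354). Crude bias = 0.5 × 0.316 × 0.354 / 0.25 = 0.224 SD (simulated 0.225).
- *Random-intercept model in that second case.* It averages a within-site slope (bias 0) and a between-site slope, weighted by information.
  - Within: 0.125 × (12.33/13.33) / 0.90 = 0.128.
  - Between: the variance of site shares is 0.125 + 0.125/13.33 = 0.134, and 0.134 / (0.90 + 13.33 × 0.10) = 0.060.
  - Between-site slope: 0.5 × 0.316 × 0.354 / 0.134 = 0.416.
  - Weighted bias: 0.060 × 0.416 / (0.060 + 0.128) = 0.133 SD (simulated 0.133).
- *Within-site contrast.* It compares cases at the same site, so the site effect cancels and this bias is zero.

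Under these inputs a random intercept leaves 0.133/0.224, or about 60%, of the site bias when sites are mixed, and all of it when sites map all or none.

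**The case against.** **The redactions.** The missing content could sit exactly where text is blacked out: a follow-up split in protocol 8.2.1 or 8.5, site handling in 8.7, either in SAP 2.5 or 2.6. This stands. Nothing here says that the plan lacks an adjustment or a follow-up split, only that none is readable.

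**The SAP already commits to the follow-up comparison.** A reader might infer that, as written, half of the comparison would yield no mapping result. The documents do not support that: SAP 1.2 and 1.4 state the follow-up comparison, 2.3.2 does not exclude a split, and 2.7 does not limit itself to what it lists. What remains is an internal mismatch that one clause could close.

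**A descriptive registry needs no model.** Description without tests is legitimate, and no readable passage attributes a difference to mapping alone. But the stated aim is to quantify the utility of mapping, and a crude table invites that reading. A caution is the minimum. An adjusted estimate shown beside the crude one serves the aim better and uses data already collected.

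**False-positive rates and coverage.** A reader might go further and claim that intervals for the mapping difference will wrongly exclude zero, or cover too rarely. No readable passage plans such an interval; those in SAP 2.2.1 and 2.2.2 are optional and concern means and percentages. That claim is not made here.

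**Conclusion.** The point holds as a mismatch between aim and readable method. The comparison of implant and follow-up characteristics by mapping is promised in five places. The readable SAP splits only the major implant characteristics, under a label that may be too narrow, and describes no more than a crude summary of a practice that follows site or physician routine. It deserves correction before analysis. It does not undermine the registry's descriptive purpose.

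The textual part depends on no assumption except that the redacted sections do not already resolve it. The size of the bias is unknown. The 0.05, 0.10 and 0.20 SD figures, and the site figures in step 3, are illustrations on assumed inputs and could be smaller or larger in practice. The direction of any bias cannot be told from the documents.

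**What to change.** First read SAP 2.5, 2.6 and the full lines in 2.7, and protocol 8.2.1 and 8.5 to 8.7. If they do not settle the matter:

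1. **Reconcile SAP 2.3.2 and 2.7 with 1.2 and 1.4.** Extend the mapping split to the 1- and 6-month follow-up characteristics. Define the mapped group and confirm that it includes left bundle branch cases.
2. **Give an adjusted estimate for a few named outcomes**, such as fluoroscopy time, skin-to-skin time and implant success.
   - Beside the crude difference, show an estimate with a 95% CI adjusted for implant indication, baseline QRS duration and conduction pattern, all collected at baseline (protocol 6.1).
   - Where sites have both mapped and unmapped cases, use a within-site contrast: site fixed effects, or a mixed model that includes the site's mapping share. A random intercept or GEE alone does not remove confounding by site.
   - Where sites map all or none, say that site and mapping cannot be separated.
   - Label 6-month lead measures as conditional on a successful implant. Protocol 6.2.1 withdraws failed implants after 30 days unless re-attempted, and 6.3 counts visits from the successful implant.
3. **Add one sentence** that differences are not attributable to mapping alone.

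The cost is a clause in 2.3.2 and 2.7, a short paragraph on the models, modest programming and no new data. Intervals will be wider, all-or-none sites add nothing to the within-site contrast, and confounding by operator remains.
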